Fondaparinux is an anticoagulant used in the prevention and treatment of thromboembolic disease. It has recently been approved in the European Union (EU) for the treatment of patients with isolated superficial vein thrombosis (SVT), i.e. without concomitant deep vein thrombosis (DVT), of the lower limbs. As part of EU approval, GlaxoSmithKline (GSK) committed to evaluate physicians' adherence to fondaparinux prescribing information regarding proper diagnosis and dosing for the treatment of SVT. This includes demonstration that physicians are prescribing fondaparinux at the recommended dose (2.5mg, or 1.5mg in patients with renal impairment), especially given the extended duration of treatment and the higher risk of bleeding which may result if the higher DVT treatment doses are used in this patient population. In addition, the study will assess whether physicians have performed a compression ultrasound (CUS), or other diagnostic imaging procedures, in order to rule out concomitant DVT, which should be treated with a higher dose (5mg, 7.5mg, 10mg).

Objective(s)

The primary objective is to evaluate physicians' adherence to fondaparinux prescribing information for the treatment of patients with SVT without concomitant DVT.

Study Design

The study is designed as a non-interventional, retrospective chart review of patients prescribed fondaparinux to treat their SVT. The study will be conducted in several EU countries. Potential investigators who have experience in the treatment of patients with SVT will be randomly identified and may include angiologists, phlebologists, vascular surgeons, etc. At each participating site, medical charts for patients with SVT treated with fondaparinux will be identified and data relating to fondaparinux dosing, use of

CUS (or other diagnostic imaging procedure) and details of the SVT will be collected. Data collection will not begin until at least six months following availability and reimbursement of the product at the particular site. This delay should be sufficient to allow fondaparinux to be adopted into routine practice and to be prescribed to a sufficient number of patients per physician.

Study Endpoints/Assessments

The primary outcome measure will be the percentage of patients for whom both an ultrasound (or other objective measure) was performed in order to rule out concomitant DVT prior to patients commencing fondaparinux therapy and who were prescribed the recommended dose (2.5mg, or 1.5mg) of fondaparinux. This will be evaluated overall and per country.

1. INTRODUCTION

1.1. Background

Superficial vein thrombosis (SVT), also termed superficial thrombophlebitis, is considered to be a common disease, even though incidence rates have not been properly assessed [1]. SVT has been reported to occur in an estimated 3-11% of the general population, associated with a higher prevalence in women, and in patients with a mean age of 60 years [2]. It is most often found in the veins of the lower limbs, but has also been reported in many other locations [2]. SVT is known to present with pain, erythema and swelling around a superficial vein that feels like a cord on palpation [2].

The main risk factors for SVT include age, varicose veins, postoperative states, pregnancy, active malignancies, immobilisation, hormone replacement therapy, auto-immune diseases, use of oral contraceptives, obesity, prolonged flights and a history of previous venous thromboembolism (VTE) [2, 3]. SVT diagnosis is based principally on clinical assessment, but the use of duplex ultrasound imaging (DUS) has enabled accurate detection of the extent and progress of the condition [2]. Treatment options available for SVT include ambulation, surgery, elastic stockings, anti-inflammatory agents and anticoagulants [2, 3].

Although once considered to be a relatively benign condition, SVT may be associated with concomitant deep vein thrombosis (DVT) and pulmonary embolism (PE). In the POST study, concomitant DVT and/or symptomatic PE was present in approximately 25% of SVT patients [4]. Patients with SVT but without concomitant DVT/PE (ie isolated SVT) are at high risk of thromboembolic complications including recurrent disease and thrombus extension into the deep veins that may lead to DVT and potentially PE. In the POST study, 8.3% of patients with isolated SVT experienced at least one symptomatic thromboembolic complication during the 3 months following diagnosis, these included 2.8% with symptomatic DVT and 0.5% with PE [4].

The anticoagulant fondaparinux (ARIXTRATM) is approved in the European Union (EU) for the prevention of VTE, in the initial treatment of acute DVT and PE, and in the treatment of acute coronary syndromes: unstable angina (UA),

non-ST-segment elevation myocardial infarction (NSTEMI) and ST-segment elevation myocardial infarction (STEMI). As of Sept 2010, fondaparinux is also approved for the treatment of adults with acute symptomatic spontaneous SVT of the lower limbs without concomitant DVT. Approval was supported by the phase III study 'Comparison of Arixtra in Lower Limb Superficial Vein Thrombosis with Placebo' (CALISTO) [5]. Patients with isolated SVT randomised to 2.5mg fondaparinux once daily for 45 days had a significantly lower risk of venous thromboembolic complications of SVT at the end of treatment, compared to those receiving placebo (relative risk reduction 85% [95%CI: 74%, 92%], p<0.001).

1.2. Rationale

Fondaparinux is an anticoagulant used in the prevention and treatment of thromboembolic disease. It has recently been approved in the European Union (EU) for the treatment of patients with isolated SVT, i.e. without concomitant DVT, of the lower limbs. As part of EU approval, GlaxoSmithKline (GSK) committed to evaluate physicians' adherence to fondaparinux prescribing information regarding proper diagnosis and dosing for the treatment of SVT. This includes demonstration that physicians are prescribing fondaparinux at the recommended dose (2.5mg, or 1.5mg in patients with renal impairment), especially given the extended duration of treatment and the higher risk of bleeding which may result if the higher DVT treatment doses are used in this patient population. In addition, the study will assess whether physicians have performed a compression ultrasound (CUS), or other diagnostic imaging procedures, in order to rule out concomitant DVT, which should be treated with a higher dose (5mg, 7.5mg, 10mg).

2. OBJECTIVE

The primary objective is to evaluate physicians' adherence to fondaparinux prescribing information for the treatment of patients with SVT of the lower limbs without concomitant DVT.

The primary endpoint of the study is the proportion of patients with isolated SVT of the lower limbs treated with fondaparinux, for whom the prescribing information was followed (i.e., an ultrasound, or other diagnostic imaging procedure, was performed in order to rule out concomitant DVT prior to patients commencing fondaparinux therapy and the correct dose of fondaparinux [either 2.5 or 1.5mg] was prescribed).

Based on the availability of data, as identified in the feasibility phase of this study, a sensitivity analysis of the primary endpoint will be conducted, incorporating the length of the thrombus (>5 cm) and/or its distance from the sapheno-femoral junction (>3 cm).

Secondary endpoints of the study include:

- The proportion of patients with SVT of the lower limbs treated with fondaparinux, for whom an ultrasound, or other diagnostic imaging procedure, was performed in order to rule out concomitant DVT prior to patients commencing fondaparinux therapy
- The proportion of patients with SVT of the lower limbs treated with fondaparinux, for whom either 2.5mg or 1.5mg fondaparinux was prescribed.

Pending the availability of the data as identified from the feasibility study, the following will also be included as secondary endpoints of the study:

 The proportion of patients with SVT of the lower limbs treated with fondaparinux, for whom the length of thrombus was measured (<5 cm being non-adherence) The proportion of patients with SVT of the lower limbs treated with fondaparinux, for whom the distance from the sapheno-femoral junction was recorded (<3 cm being non-adherence).

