3.3. Patient inclusion and exclusion criteria

3.3.1. Inclusion Criteria

- (1) Diagnosis of SVT
- (2) Prescribed fondaparinux for the treatment of SVT
- (3) Age 18 years or older.

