4.3. Outcome

The primary outcome measure will be the proportion of patients for whom **both** an ultrasound (or other diagnostic imaging procedure), was performed in order to rule out concomitant DVT prior to patients commencing fondaparinux therapy **and** that the correct dose of fondaparinux (2.5mg or 1.5mg) was prescribed (i.e. adherence to fondaparinux prescribing information – see Appendix 9.1). This will be evaluated overall and in each country.

A sensitivity analysis of the primary outcome will be conducted incorporating the length of the thrombus (>5 cm) and/or its distance from the sapheno-femoral junction (>3 cm), pending the availability of the data.

Secondary outcomes will evaluate the proportion of patients prescribed the correct dose of fondaparinux, as well as those who had an ultrasound (or other diagnostic imaging procedure) performed to rule out concomitant DVT. In addition, when available, the proportion of patients having a thrombus >5 cm and a distance from the sapheno-femoral junction of at least 3 cm will be estimated.

Similar to the primary outcome, these will also be evaluated overall and in each country.

Please note that patient outcome data following fondaparinux prescription will not be collected.

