5.2.1. Primary Analyses

Adherence estimates with confidence intervals will be derived using generalised estimating equations (GEE) overall and for each country [8]. The GEE will explicitly take into account the nesting of patients, per physician, within a medical practice.

Adherence in the current study will be defined as performing CUS, or other diagnostic imaging procedure, in order to rule out concomitant DVT prior to patients commencing fondaparinux therapy and ensuring that the recommended dose of fondaparinux is prescribed.

A sensitivity analysis will be conducted incorporating the length of the thrombus and the distance of the thrombus from the sapheno-femoral junction into the primary endpoint if the data is available.

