9.3 Case Report Form

·			OFFICE U	SE ONLY
Superficial Vein Thrombosis (SVT): Case	Record Fo	rm	Doctor Number	Patient Number
Today's date:			 (dd/mm/y	ууу)
Date patient first presented with symptoms:			(dd/mm/y	
Date patient mot precented with symptome.		_ /	(aa/111111/y	,,,,,
Date patient diagnosed:	/	_/	(dd/mm/y	ууу)
Fondaparinux prescribing				
Date fondaparinux first prescribed:	/	_/	(dd/mm/y	yyy)
Fondaparinux dose initially prescribed:	mg			
Planned duration of fondaparinux treatment:	da	ays 🗌 w	veeks (please ✓ if	days or weeks)
Diagnosis				
Was SVT confirmed through imaging?	☐ Yes ☐ N	lo		
If yes, what diagnostic imaging, was performed on	this patient?			
☐ Ultrasound ☐ Venography ☐ C	T Scan	☐ MF	RI	
Other (specify:)			
If 'No', please state how SVT was confirmed:				
If imaging was not performed, please state why:				
Please state location of the SVT:	☐ Left lower	limb □R	ight lower limb	
Please state position of the SVT:	 ☐ Great saph		Lesser saph	enous
·	☐ Tributary		r (
Diagon state length of the CVT			om 🗆 Not	rocarded
Please state length of the SVT:			_	recorded
Please state diameter of the SVT:			_	recorded
Please state distance from sapheno-femoral junctic	Of 1	_ · (cm Not	recorded
Was DVT diagnosed?	☐ Yes ☐ N	lo [Imaging not p	erformed
Was symptomatic PE diagnosed?	☐ Yes ☐ N	lo		

[figure not shown]
OFFICE USE ONLY							
Doctor Number	Patient Number						

Superficial Vein Thrombosis (SVT): Case Record Form

Patient demographics						
Age:	years					
Weight:	Kg					
Gender	☐ Female ☐ Male					
Patient history						
Is there documented evidence that this patient has	renal impairment?:					
	☐ Yes ☐ No ☐ Do not know					
If Yes, Mild Moderate Severe Do	not know					
Serum Creatinine result:	µm/L					
	☐ Not assessed					
Date last calculated	/					
Creatinine Clearance result:	ml/min					
	☐ Not assessed					
Date last calculated	/					
Has this patient been previously treated for DVT, PE and/or SVT?						
	□DVT □PE □SVT					

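### The primary adherence proportion has no single denominator, and no rule says how un-imaged or DVT-positive patients are scored

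*Supplement*

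**What the plan says.** Section 2 gives the primary endpoint: "The primary endpoint of the study is the proportion of patients with isolated SVT of the lower limbs treated with fondaparinux". What is counted among them is adherence to the label. The secondary endpoints in the same section drop the word isolated, for example: "The proportion of patients with SVT of the lower limbs treated with fondaparinux, for whom either 2.5mg or 1.5mg fondaparinux was prescribed".

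Section 4.3 opens with "The primary outcome measure will be the proportion of patients for whom" and sets no DVT condition on who is counted. The endpoint paragraph of the summary does the same. Inclusion criterion 1 (section 3.3.1) reads in full "Diagnosis of SVT", and the only exclusion criterion concerns trial participation.

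The scoring rule in section 5.2.1 begins: "Adherence in the current study will be defined as performing CUS, or other diagnostic imaging procedure, in order to rule out concomitant DVT". It adds that imaging must precede treatment and that the recommended dose is prescribed. The summary and sections 2 and 4.3 state the same two components.

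The CRF (Appendix 9.3) asks "Was DVT diagnosed", with answers for yes, no and no imaging done. The only locations it offers for the SVT are the left and right lower limb.

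**The concern.** Two groups of patients decide the result, and the protocol places neither.

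The first is patients who were not imaged. They fail the imaging component, so they are the main source of non-adherence. On the CRF they have no DVT = No entry. If a programmer turns isolated into a filter on DVT = No, they leave the denominator.

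The second is patients whose scan showed DVT. The rule asks whether imaging was done with the aim of ruling out DVT, not whether DVT was ruled out. The standard being measured (Appendix 9.1, prescribing information) requires DVT to have been excluded before treatment, and section 1.2 speaks of "concomitant DVT, which should be treated with a higher dose (5mg, 7.5mg, 10mg". The DVT answer is collected but has no role in the score.

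This single proportion is the main result of a study that answers a regulatory commitment on diagnosis and dosing. As written, it depends on which section the programmer follows.

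**Working it through.** **1. The plan's own figures.** The documents give no expected adherence by denominator, only power. For the minimum sample (19 physicians with 7 patients each, ICC 0.3), Table 3 states 0.804. A simulation of 10,000 runs used correlated binary data with p = 0.8, an intercept-only logit GEE with robust variance, and success defined as a lower 95% limit above 60%. It gives 0.824. Of the 16 cells in Table 3, 13 agree within 2 points and the other three come out 2.1 to 3.2 points above the stated value. The power is not in dispute, but it assumes that all 133 or 210 patients are analysed.

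**2. The sections side by side.**

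| Place | Who is counted | DVT result used? |
|---|---|---|
| Section 2, primary | lower-limb SVT, isolated | only through the word isolated |
| Section 2, secondary | lower-limb SVT | no |
| Summary; section 4.3 | patients | no |
| Section 5.2.1 | not stated | no |
| Section 3.3.1 (eligibility) | any SVT | no |

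**3. Reading (a): isolated means DVT = No on the CRF.** Let q be the share imaged before treatment and c the share on 2.5 or 1.5 mg. Both are assumptions, taken as independent, with no DVT-positive patients.

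- All patients: q × c = 0.85 × 0.94 = 0.799.
- DVT = No only: c = 0.94, whatever q is.
- Gap: c × (1 − q) = 0.94 × 0.15 = 14.1 points. It is 28.2 points at q = 0.70 and 4.7 points at q = 0.95.

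The imaging secondary endpoint, in all lower-limb SVT, would be 85%. A composite of imaging and dose would then be reported at 94%, above one of its own components.

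**4. Reading (b): all SVT patients, rule as written.** Patients scored adherent despite a scan showing DVT make up q × d × s, where d is the DVT share of those imaged and s the share of these on 2.5 or 1.5 mg (both assumed).

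- 0.85 × 0.05 × 0.50 = 2.1 points.
- d from 2% to 10%, s = 50%: 0.9 to 4.3 points.
- s from 0 to 100%, d = 5%: 0 to 4.3 points.

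**5. One consistent example.** Take q = 85%, d = 5%, s = 50%, and 94% of imaged patients on 2.5 or 1.5 mg. The share among imaged DVT-negative patients is then (0.94 − 0.05 × 0.5) / 0.95 = 0.915 / 0.95 = 96.3%.

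| Rule | Estimate |
|---|---|
| DVT = No only (reading a) | 96.3% |
| All SVT, DVT result ignored (reading b) | 0.85 × 0.94 = 79.9% |
| No recorded DVT, un-imaged kept as non-adherent | 0.85 × 0.915 / (1 − 0.85 × 0.05) = 0.778 / 0.9575 = 81.2% |
| All SVT, DVT = Yes never adherent | 0.85 × 0.915 = 77.8% |

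Reading (a) would keep 0.85 × 0.95 = 81% of patients: about 107 of 133, or 170 of 210.

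**6. Effect on the 60% planning benchmark (section 5.1).** Assume 70% imaged, 95% on 2.5 or 1.5 mg, no DVT, ICC 0.2 and 30 physicians with 7 patients each.

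- All patients: 0.70 × 0.95 = 66.5%. Design effect 1 + 6 × 0.2 = 2.2. SE = √(0.665 × 0.335 × 2.2 / 210) = 0.048. Lower limit about 57%.
- DVT = No only: 147 patients, 4.9 per physician. Design effect 1 + 3.9 × 0.2 = 1.78. SE = √(0.95 × 0.05 × 1.78 / 147) = 0.024. Lower limit about 90%.

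The same charts fall below the benchmark under one reading and clear it under the other.

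**The case against.** The best defence is that isolated is a clinical label. Section 1.2 explains it as SVT without concomitant DVT, not as imaging-confirmed. The site survey asks for counts of isolated SVT separately from how SVT is diagnosed, and section 1.1 says that diagnosis is mainly clinical. On that view un-imaged patients with no recorded DVT stay in as non-adherent. This fits the rest of the plan: an imaging component would have little purpose if un-imaged patients left, the CRF asks why imaging was not done, and the sample size counts everyone. This stands as a sensible reading, and the fix adopts it. It does not remove the point, because the protocol never says so.

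It can also be said that eligibility criteria are not an analysis denominator, and that section 4.3 may be shorthand for section 2. Both are fair. So is the remark that no SAP is shown and that coding detail commonly belongs there. The point therefore rests on the conflict within the protocol, not on missing detail.

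A reader might infer more than the documents support:

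- **Both defects at once.** They belong to different readings. Under DVT = No, DVT-positive patients are outside the denominator. Under all SVT, un-imaged patients stay in and fail.
- **An imaging component of 100% by construction.** The rule also requires imaging before treatment, so late imaging still fails, and the imaging secondary endpoint would still reveal a low rate.
- **An error of about 11 points under reading (b), from the 25% in section 1.1.** That figure covers DVT and/or symptomatic PE in SVT patients generally, not those prescribed fondaparinux for SVT. With half on other doses, 0.85 × 0.25 × 0.5 = 10.6% of all patients would be on other doses, against at most 6% if 94% are on 2.5 or 1.5 mg.

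**Conclusion.** The point holds as a conflict over the denominator and a gap in the scoring rule. Section 2 restricts the primary endpoint to isolated SVT, section 4.3 and the summary do not, and no statement of the rule uses the DVT result.

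The larger risk is reading (a): an upward bias of about 14 points at 85% imaged and 94% on 2.5 or 1.5 mg, and of 5 to 28 points for imaging rates from 95% down to 70%. Reading (b) is smaller: about 2 points at 85% imaged, 5% DVT and half of these on 2.5 or 1.5 mg, with a range of 0 to about 4. The imaging, dosing and DVT shares are assumptions; the documents give none for this population. The direction under each reading does not depend on them.

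Sections 1.2, 2, 4.3 and 5.2.1 and the prescribing information in Appendix 9.1 must be reconciled. No view is taken on which dose is right.

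**What to change.** State one primary definition, identically in sections 2, 4.3 and 5.2.1 and in the summary:

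- **Denominator:** patients with lower-limb SVT who were prescribed fondaparinux for SVT and have no recorded DVT. Patients coded as not imaged stay in and count as non-adherent.
- **DVT = Yes patients:** tabulate them separately by prescribed dose from the existing CRF item.
- **Sensitivity analysis:** repeat the estimate with the DVT = Yes patients in the denominator and not counted as adherent.
- **Eligibility:** add the lower-limb condition to inclusion criterion 1, so that it matches section 2 and the CRF.

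The cost is protocol wording and one extra table. No new data item is needed.

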3.3.2. Exclusion Criteria

(1) Patients should not have been involved in any clinical trial that could influence SVT treatment during the observational period (i.e. the retrospective period during which data is recorded).

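### The secondary dose endpoint is set in all lower-limb SVT while the primary is set in isolated SVT, so patients with concomitant DVT are scored against the rationale and can move the dose rate in either direction

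*Supplement*

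**What the plan says.** Section 2 gives the primary endpoint as "the proportion of patients with isolated SVT of the lower limbs treated with fondaparinux, for whom the prescribing information was followed". The secondary dose endpoint in the same section is "The proportion of patients with SVT of the lower limbs treated with fondaparinux, for whom either 2.5mg or 1.5mg fondaparinux was prescribed". The word isolated is absent from it, and only 2.5 mg or 1.5 mg counts as success. The imaging component endpoint is likewise set in SVT of the lower limbs.

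Section 1.2 describes imaging as done "in order to rule out concomitant DVT, which should be treated with a higher dose (5mg, 7.5mg, 10mg").

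Eligibility (Section 3.3) asks for a diagnosis of SVT, age 18 or over, and "Prescribed fondaparinux for the treatment of SVT". The only exclusion is "Patients should not have been involved in any clinical trial that could influence SVT treatment during the observational period". The case report form (Appendix 9.3) asks "Was DVT diagnosed" and offers yes, no, or imaging not performed. Section 4.4 lists presence or absence of DVT among the data to be collected.

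The Protocol Summary, Section 4.3 and Section 5.2.1 restate the primary outcome without limiting it to isolated SVT. Sections 4.3 and 5.2.2 restate the dose outcome with no rule for patients who have DVT.

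**The concern.** The sponsor's commitment, set out in Section 1.2, is to show whether the higher DVT doses are being used in patients with isolated SVT. The dose endpoint isolates that question. As defined, it cannot separate a DVT dose given in isolated SVT from one given because DVT was found. It also credits a DVT-positive patient on 2.5 or 1.5 mg, although the rationale places DVT in the higher-dose group. Both kinds of patient enter a rate that will be read as dosing adherence in isolated SVT.

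The primary endpoint combines the imaging and dose components. If it has a different denominator from theirs, the component rates cannot be set beside the primary rate to show where adherence is lost.

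**Working it through.** **The plan's own figures.** The documents give no expected value for the dose endpoint. Their only quantitative claims are the power figures for the composite. For 30 physicians with 7 patients each and ICC 0.2, simulation gave 0.984 against the stated 0.974. Of the 16 cells in Table 3, 13 agree within 2 points and the other three come out 2.1 to 2.9 points above the stated value. These figures do not bear on the present point.

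**How the stated rule scores each patient**

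| Patient | Dose prescribed | Dose endpoint as written | Section 1.2 |
|---|---|---|---|
| Isolated SVT | 2.5/1.5 mg | success | consistent |
| Isolated SVT | higher | failure | consistent |
| Concomitant DVT | higher | failure | contradicts |
| Concomitant DVT | 2.5/1.5 mg | success | contradicts |

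**Inputs.** All three are assumptions:
- f, the share of sampled charts with concomitant DVT: 5%, 10% or 25%. Section 1.1 says that in a cited cohort "concomitant DVT and/or symptomatic PE was present in approximately 25% of SVT patients". That covers DVT and/or PE in SVT patients generally, not in charts of patients prescribed fondaparinux for SVT, so 25% is only an illustrative upper value.
- p_iso, the share of isolated-SVT patients on 2.5/1.5 mg: 0.95. Patients who were not imaged are counted here.
- q, the share of DVT-positive patients on 2.5/1.5 mg: 0, 0.5 or 1.

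**Formula.** Scored rate = (1 − f) × p_iso + f × q. The shift from the isolated-SVT rate is therefore f × (q − p_iso).

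| f | q = 0 | q = 0.5 | q = 1 |
|---|---|---|---|
| 5% | 90.25% (−4.75) | 92.75% (−2.25) | 95.25% (+0.25) |
| 10% | 85.5% (−9.5) | 90.5% (−4.5) | 95.5% (+0.5) |
| 25% | 71.25% (−23.75) | 83.75% (−11.25) | 96.25% (+1.25) |

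With p_iso = 0.80 and f = 10%, the shifts are −8, −3 and +2 points. The sign depends only on whether q is below or above p_iso.

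**A second benchmark.** Suppose each patient were scored by the rationale's own dose distinction. DVT-positive patients would contribute f × (1 − q) instead of f × q, so the error is f × (2q − 1). At f = 10% that is −10, 0 and +10 points for q = 0, 0.5 and 1. The two misclassifications can cancel in the total while both are present.

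**Yardstick.** The design effect at 7 patients per physician and ICC 0.2 is 1 + 6 × 0.2 = 2.2. At p = 0.80 the 95% half-width is 1.96 × √(0.16 × 2.2 / 840) = 0.040 pooled and 1.96 × √(0.16 × 2.2 / 210) = 0.080 per country. At p = 0.95 it would be narrower: 1.96 × √(0.0475 × 2.2 / 840) = 0.022 and 1.96 × √(0.0475 × 2.2 / 210) = 0.044.

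**The case against.** **The second inclusion criterion filters this group.** A patient dosed for DVT may be recorded as treated for DVT and never sampled. This stands as a reason why f is unknown and may be small. It does not close the gap: the criterion does not require isolated SVT, the form provides for a DVT diagnosis, and the form as reproduced shows no item for treatment indication against which to check the filter.

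**One population was probably meant.** The objective refers to SVT without concomitant DVT, three other places state the primary outcome without the word isolated, and Section 5.2.2 applies the primary methodology to the secondary endpoints. It is true that the contrast appears only in Section 2. But the other places make the primary population inconsistent rather than settled, and a shared estimation method sets no denominator. Analysis sets are often left to an analysis plan, and none is shown. Here, though, the complaint is about a stated scoring rule, not a missing detail.

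**The effect may be within sampling error.** With f = 5% and q = 0.5, the shift of −2.25 points lies inside the pooled half-width of 4. With f = 10% and q = 0.5, −4.5 lies inside the per-country half-width of 8. Both statements are correct at p = 0.80.

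**The DVT item is undated.** A yes could record a DVT found after prescribing. This is a minor limitation, since the item sits in the diagnosis block of a study that collects no later outcomes.

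**The stronger reading.** A reader might infer that the dose rate is biased downward, perhaps by more than 20 points. The documents do not support that. It would require DVT-positive charts to be sampled in number and to carry 2.5/1.5 mg less often than isolated-SVT charts. Section 1.2 makes that pattern plausible, but neither f nor q is given, and the upward error is built into the same definition.

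**Conclusion.** The contradiction is established from the text. Section 2 uses two populations, nothing in Section 3.3 removes concomitant DVT, and the dose endpoint scores DVT-positive patients opposite to the distinction in Section 1.2, whichever dose they received. The direction and size of the resulting error are not established. It is downward if DVT patients receive 2.5/1.5 mg less often than isolated-SVT patients, and upward if more often. With p_iso = 0.95 and f = 10%, both assumed, it runs from −9.5 to +0.5 points. At the lower end it exceeds the sampling half-width both pooled and per country.

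The endpoint is secondary and descriptive, and the 60% bound in Section 5.1 belongs to the composite. The point should still be settled before the data are seen, because this endpoint answers the regulatory question most directly and the correction is nearly free. No view is taken on which dose is right.

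**What to change.** 1. State one analysis population, isolated SVT of the lower limbs, for the primary and component endpoints, in the same words in the Protocol Summary and in Sections 2, 4.3, 5.2.1 and 5.2.2.
2. Compute the dose rate excluding charts where the DVT item is yes. Keep both no and imaging not performed, and show them separately. Dropping the patients who were not imaged would remove the imaging failures from the composite's denominator.
3. State how charts with symptomatic PE are handled. Section 1.1 describes isolated SVT as without DVT or PE, whereas Section 1.2 mentions DVT only.
4. Tabulate the prescribed doses of DVT-positive patients descriptively, outside the adherence rate.
5. Reconcile Sections 1.2 and 2 on how this group is treated in the endpoints.

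The cost is wording in five places, one extra table and a slightly smaller denominator. If f were 10%, the pooled target would fall from 840 to 756, or 6.3 patients per physician. The design effect would be 1 + 5.3 × 0.2 = 2.06 and the half-width 1.96 × √(0.16 × 2.06 / 756) = 0.041, against 0.040. No new data are needed.
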